6.1.10. Partial Remission (IgAN Cohort Only)

Partial remission will be defined as mean proteinuria < 1 g/24 hours based on 2 valid 24-hour urine collections obtained within 2 weeks prior to the study visit (Week 26 or 50).

Only central laboratory results from both scheduled and unscheduled visits will be used to assess partial remission.

In the presence of missing central laboratory values, the following rules will be applied:

- If only 1 nonmissing 24-hour urine collection is available at the visit, then this value will be used for analysis.
- If both collections are missing at the visit, then partial remission will be treated as missing.

6.1.11. Partial Renal Response (LN Cohort Only)

To achieve PRR, participants who did not achieve CRR in the LN cohort must meet all of the following criteria:

- A decrease in UPCR ≥ 50% compared to the baseline value based on mean of two 24-hour urine collections obtained within 2 weeks prior to the study visit (Week 26 or 50)
- eGFR > 60 mL/min/1.73 m² or no eGFR reduction ≥ 20% from the baseline value based on the mean of 2 values. The first eGFR value must be obtained within 2 weeks prior to the study visit (Week 26 or 50) and the second eGFR value will be obtained on the study visit (Week 26 or 50)
- No treatment failure

Only central laboratory results from both scheduled and unscheduled visits will be used to assess PRR.

In the presence of missing central laboratory values, the following rules will be applied:

- If only 1 nonmissing collection is available at the visit, then this value will be used for analysis.
- If both collections are missing at the visit, then PRR will be treated as missing.

Treatment failure is defined as the receipt of additional standard of care therapy at any time up during the study for protocol-defined renal flare, severe extrarenal SLE flare, or suboptimal response. Therefore, no treatment failure will be determined as the absence of additional standard of care therapy received at any time (Week 26 or 50) as recorded on the Additional Standard-of-Care Therapy eCRF.

6.1.12. Serum Creatinine and Estimated Glomerular Filtration Rate

Serum creatinine measurements are not reliable with concurrent dialysis. Therefore, all serum creatinine values obtained while a participant is on dialysis will be excluded from all analyses. eGFR will be imputed with a value of 10 (mL/min/1.73 m²) while a participant is on dialysis. A participant will be considered on dialysis from the first day of dialysis through 5 days after the end of dialysis. This rule will only be applied to post-Baseline assessments of serum creatinine and eGFR.

6.2. Study and Participant Characteristics

6.2.1. Study Participants

A summary of enrolled participants, including the number and percentage of participants by region, country, and site, will be presented by treatment group and overall.

In addition, a summary of participants who did not satisfy the inclusion/exclusion criteria will be presented by treatment group and overall.

A summary of participant disposition will include the number and percentage of participants who completed the study or discontinued from the study (along with the primary reason for discontinuation) will be presented. Discontinuation status will be presented overall as well as separately for discontinuations impacted by COVID-19. Number of participants who experienced dosing pause will also be presented. Participant disposition will be presented separately for overall, 26-week Blinded Initial Evaluation Period, 24-week Blinded Extended Treatment Period, and 2-year OLE Period.

The number and percentage of participants in each defined analysis set will also be presented. A summary of enrolled participants by region will be presented by treatment group and overall.

Participants who are randomized but did not satisfy the inclusion/exclusion criteria will be presented by treatment group and overall for each criterion not satisfied.

By-participant data listings for disposition and analysis populations will be provided as well as a listing of participants who did not satisfy the inclusion/exclusion criteria.

6.2.2. Demographics and Baseline Characteristics

All demographic and baseline disease characteristics will be summarized using the FAS. Summary statistics will be presented by treatment group and overall for each disease cohort.

By-participant listings of these data will also be provided.

6.2.2.1. Demographics

The following demographic variables will be summarized:

- Sex
- Race
- Ethnicity
- Age at Screening (years): descriptive statistics (n, mean, median, SD, minimum, maximum) and by frequency of participants in each age category: 18 to 65 years,
 > 65 years
- Baseline weight (kg): descriptive statistics (n, mean, median, SD, minimum, maximum) and frequency of participants in the following categories: < 60 kg, 60 to < 100 kg, ≥ 100 kg
- Baseline height (cm)

- Baseline body mass index (kg/m²)
- Geographical region (North America, Latin America, Europe, and Asia Pacific)

6.2.2.2. Baseline Disease Characteristics

The following baseline disease characteristic will be summarized:

- Duration of disease (years): descriptive statistics (n, mean, median, SD, minimum, maximum)
- Baseline eGFR (mL/min/1.73m²): descriptive statistics (n, mean, median, SD, minimum, maximum) and frequency of participants in the following categories: <= 60, > 60-90, > 90
- Baseline C3: descriptive statistics (n, mean, median, SD, minimum, maximum) and frequency of participants with low C3
- Baseline C4: descriptive statistics (n, mean, median, SD, minimum, maximum) and frequency of participants with low C4
- Baseline serum albumin: descriptive statistics (n, mean, median, SD, minimum, maximum)
- Baseline SF-36 score: descriptive statistics (n, mean, median, SD, minimum, maximum)
- Baseline EQ-5D-5L: descriptive statistics (n, mean, median, SD, minimum, maximum)

For the LN cohort, the following additional disease characteristics will be summarized:

- Time from eligibility biopsy to randomization (< 1 month, 1-3 months, 3-6 months, > 6 months)
- LN class based on central pathology (III or III/V, IV or IV/V)
- LN class based on local pathology (III or III/V, IV or IV/V)
- Glomerular C3 staining based on central pathology (0+, 1+, 2+, 3+)
- Glomerular C1q staining based on central pathology (0+, 1+, 2+, 3+)
- Tubulointerstitial C3 staining based on central pathology (0+, 1+, 2+, 3+)
- Tubulointerstitial C1q staining based on central pathology (0+, 1+, 2+, 3+)
- Vascular C3 staining based on central pathology (0+, 1+, 2+, 3+)
- Vascular C1q staining based on central pathology (0+, 1+, 2+, 3+)
- Renal biopsy activity index based on central pathology: descriptive statistics (n, mean, median, SD, minimum, maximum)
- Renal biopsy chronicity index based on central pathology: descriptive statistics (n, mean, median, SD, minimum, maximum)
- TMA on renal biopsy based on central pathology (yes, no)

- Baseline 24-hour UPCR: descriptive statistics (n, mean, median, SD, minimum, maximum) and frequency of participants in the following categories: ≤ 3.5 g/g,
 > 3.5 g/g
- Baseline spot UPCR: descriptive statistics (n, mean, median, SD, minimum, maximum) and frequency of participants in the following categories: ≤ 3.5 g/g, > 3.5 g/g
- Baseline disease status (naïve, relapse)
- Corticosteroid induction timing (prior to Screening, during Screening Period)
- Baseline SLEDAI-2K SELENA Modification score: descriptive statistics (n, mean, median, SD, minimum, maximum)
- Baseline FACIT-Fatigue score: descriptive statistics (n, mean, median, SD, minimum, maximum)
- Baseline anti-dsDNA autoantibodies: descriptive statistics (n, mean, median, SD, minimum, maximum) and frequency of participants with antibody levels < LLN
- Baseline anti-C1q autoantibodies: descriptive statistics (n, mean, median, SD, minimum, maximum) and frequency of participants with antibody levels < LLN
- Concomitant therapy with SGLT-2 inhibitors (Yes, No)

For the IgAN cohort, the following additional disease characteristics will be summarized:

- Baseline 24-hour urine protein (g/day): descriptive statistics (n, mean, median, SD, minimum, maximum) and frequency of participants in the following categories:
 (1-2 g/day, > 2 g/day)
- Baseline 24-hour UPCR (g/g): descriptive statistics (n, mean, median, SD, minimum, maximum)
- Time from eligibility biopsy to randomization (< 1 month, 1-3 months, 3-6 months, 6-12 months, 12-24 months, > 24 months)
- MEST-C score based on central pathology (M0, M1, E0, E1, S0, S1, T0, T1, T2, C0, C1, C2)
- C3 staining based on central pathology (0+, 1+, 2+, 3+)
- Clq staining based on central pathology (0+, 1+, 2+, 3+)
- Concomitant therapy with SGLT-2 inhibitors (Yes, No)

The agreement between local and central pathology diagnosis will be assessed for each disease cohort by inter-rater reliability analysis using the kappa statistic reported with Cohen's K-coefficient and its 95% CIs. In addition, if central pathology results are limited, then local pathology results may be summarized as well in the disease characteristic summary.

6.2.3. Medical History

Medical history will be summarized using MedDRA, version 26.1 or later, SOC and PT by treatment group and overall for each disease cohort separately for the SS.

By-participant listings of medical/surgical history and abnormal physical examinations will also be produced.

6.2.4. Prior and Concomitant Medications

Prior and concomitant medications and procedures will be summarized using the SS.

Prior medications and/or vaccines (including vitamins, herbal preparations, and those discussed in the eligibility criteria in Protocol Section 5) and procedures (eg, surgery, biopsy, physical therapy) are those received or underwent ≤ 30 days prior to Screening or during the Screening Period, as well as any meningococcal vaccine administered within the last 3 years.

Concomitant medications (including any medication, vitamin, herbal preparation, or supplement) and procedures defined in Protocol Section 6.5) are those received on or after the first study intervention date (Day 1), including those started before Day 1 and continued after Day 1.

Medications will be coded using the World Health Organization Drug Dictionary (WHO-DRUG) version in use by Alexion at the time of the analysis, while nonpharmacologic therapies and procedures (any therapeutic intervention, such as surgery/biopsy or physical therapy) will be coded using MedDRA version 26.1 or later.

Prior medication and concomitant medication, summaries will be presented by WHO-DRUG anatomical therapeutic chemical (ATC) Level 3 and by WHO-DRUG generic name using number and percentage of participants by treatment group. Procedures will be summarized similarly but presented by MedDRA Class and PT. In addition, protocol-required vaccinations will be summarized similarly.

By-participant listings of prior and concomitant medications, procedures, and protocol-required vaccinations will also be produced.

6.2.5. Allowed Concomitant and Additional Standard of Care Therapy

Background and additional standard of care therapy medications will be summarized using the SS.

Allowed concomitant therapy for participants in the LN cohort consist of standard of care treatment for induction and maintenance treatment of LN including corticosteroids and MMF or MMF equivalent. In the LN cohort, participants will receive additional standard of care therapy in the event of a protocol-defined renal flare, severe extrarenal SLE flare, or suboptimal response. Additional standard of care therapy is defined as intensification of current standard of care or introduction of new immunosuppressive therapies. Additional standard of care therapy will be presented by WHO-DRUG ATC Level 3 and by WHO-DRUG generic name by type of flare using number and percentage of participants by treatment group.

Allowed concomitant therapy for participants in the IgAN cohort consist of standard of care treatment including maximally tolerated dose of RAS-blocking agents such as angiotensin-converting enzyme (ACE) inhibitors or angiotensin II receptor blockers (ARBs).

Allowed concomitant therapy use within 3 months prior to Screening and up to the first dose of study intervention will be presented by WHO-DRUG ATC Level 3 and by WHO-DRUG generic name using number and percentage of participants by treatment group. In addition, allowed concomitant therapy use at baseline will be summarized by treatment group. Changes in allowed concomitant therapy use during the study as well as the reason for change will be summarized by treatment group.

By-participant listings of allowed concomitant therapy and additional standard of care therapy will also be produced.

6.2.6. Protocol Deviations

The number and percentage of participants with specific protocol deviations will be summarized for all enrolled participants by important and nonimportant deviations. Protocol deviations will be presented overall as well as separately for those related to COVID-19.

Summary statistics will be presented by treatment group and overall.

6.3. Instrument Scoring Details

6.3.1. SF-36

The SF-36 version 2 is a set of generic, coherent, and easily administered QoL measures. It has 36 items grouped in 8 dimensions. It measures each of the following 8 health domains: Physical Functioning, Social Functioning, Role Limitations Due to Physical Health, Bodily Pain, General Health, Mental Health, Role Limitations Due to Emotional Problems, and Vitality. Eight health domain scores and 2 component scores (PCS and MCS) will be calculated.

The SF-36 version 2 Health Survey with the standard (4-week) recall period will be used in this study. The OPTUM PRO CoRE 1.5 Smart Measurement System will be used to derive the 8 domain scores and 2 component scores. The algorithms used by the software are described below (as excerpted from the User's Guide).

6.3.1.1. Data Cleaning and Item Recoding

First, the data are checked for out-of-range values. Out-of-range values are any values that are outside the range of acceptable item response values for the SF-36 version 2 Health Survey. Out-of-range values will be converted to missing values. Next, 10 items (BP01, BP02, GH01, GH03, GH05, VT01, VT02, SF01, MH03, MH05) are reverse-scored. Reverse scoring of these items is required so that a higher item response value indicates better health for all SF-36 version 2 Health Survey items and summary measures.

6.3.1.2. Item Recalibration

For most of the SF-36 version 2 Health Survey items, research to date offers good support for the assumption of a linear relationship between the item scores and the underlying health concept defined by their scales. However, empirical work has shown that 2 items, GH01 and BP01, require recalibration to satisfy this important scaling assumption. The Bodily Pain scale requires additional scoring rules because the items offer both different numbers and different content of

response choices and administration of item BP02 depended upon the response to an item like item BP01 in past studies.

6.3.1.3. Computation of Raw Scale Scores

After recoding and recalibrating the required item values, a raw score is computed for each scale. This score is the simple algebraic sum of the final values for all items in that scale.

6.3.1.4. Transformation of Raw Scale Scores to 0 to 100 Scale

The next step involves transforming each raw scale score to a 0 to 100 scale. This transformation converts the lowest and highest possible scores to zero and 100, respectively. Scores between these values represent the percentage of the total possible score achieved.

6.3.1.5. Transformation of 0 to 100 Scores to T-Score-Based Scores

The first step in T-score based scoring consists of standardizing each SF-36 version 2 Health Survey scale using a z-score transformation. A z-score indicates how far a score deviates from the mean in standard deviation units. The z-score for each scale is computed by subtracting the mean 0 to 100 score observed in the 2009 general US population from each SF-36 version 2 Health Survey scale score (0 to 100) scale and dividing the difference by the corresponding scale standard deviation observed in the 2009 general US population. The means and standard deviations utilized are dependent upon the recall period option chosen by the user, based on the SF-36 version 2 Health Survey form used to collect the data being scored.

The next step of the T-score based scoring is to linearly transform each SF-36 version 2 Health Survey z-score to have a mean score of 50 and a standard deviation of 10. This is done by multiplying each SF-36 version 2 Health Survey z-score by 10 and adding the resulting product to 50. These are referred to as "norm-based" scores. The norm-based scores will be used for the 8 domain scores.

6.3.1.6. Scoring the SF-36 Version 2 Healthy Survey Component Summary Measures

The first step in scoring the component summary measures consists of standardizing each SF-36 version 2 Health Survey scale using a z-score transformation. The z-score for each scale is computed by subtracting the mean 0 to 100 score observed in the 2009 general US population from each SF-36 version 2 Health Survey scale score (0 to 100) scale and dividing the difference by the corresponding scale standard deviation observed in the 2009 general US population. The means and standard deviations utilized are dependent upon the recall period option chosen by the user based on the SF-36v2 Health Survey form used to collect the data being scored.

After a z-score has been computed for each SF-36 version 2 Health Survey scale, the second step involves computation of aggregate scores for the physical and mental summaries using weights (factor score coefficients) derived from the 1990 general US population. These are the same weights as those used to score PCS and MCS from the SF-36 version 2 Health Survey. An aggregate physical score is computed by multiplying the z-score of each SF-36 version 2 Health Survey scale by its associated physical factor score coefficient and summing the 8 products. If any of the scale scores are missing, then the aggregate physical score is not computed. An aggregate mental score is computed by multiplying the z-score of each SF-36 version 2 Health

Survey scale by its associated mental factor score coefficient and summing the 8 products. If any of the scale scores are missing, then the aggregate mental score is not computed.

The third step involves transforming the aggregate physical and mental summary scores to the T-score based (50, 10) scoring. This is done by multiplying each aggregate summary score obtained from the second step by 10 and adding the resulting product to 50.

6.3.1.7. Handling of Missing Items

The maximum data recovery option will be used for missing data estimation. This results in the application of algorithms that compute a scale score for those respondents who have answered at least 1 item that represents that construct. For the Physical Functioning scale, item parameters obtained through item response theory methods are used to estimate a missing value on an item based upon a respondent's responses to answered items. For the 7 remaining scales, a person-specific estimate based on the mean response to the answered items on the scale is used to estimate a missing value. Additionally, a PCS and MCS score is calculated for those respondents who have calculated scores on at least 7 of the 8 SF-36 version 2 Health Survey scales. However, PCS is not estimated if the Physical Functioning scale is missing, and MCS is not estimated if the MH scale is missing.

6.3.2. Five-Level EuroQol-5 Dimension (EQ-5D-5L)

The EQ-5D-5L version will be used in this study. EQ-5D health states, defined by the EQ-5D descriptive system, may be converted into a single summary index by applying a formula that attaches values (also called weights) to each of the levels in each dimension. The index can be calculated by deducting the appropriate weights from 1, the value for full health (ie, state 11111). The collection of index values (weights) for all possible EQ-5D health states is called a value set. EQ-5D-5L index scores for this study will be obtained using the composite time trade-off (cTTO) method based on the Tobit model (Pickard, 2019). The calculation is illustrated in Table 8.

Table 8: EQ-5D-5L cTTO Calculation

US cTTO		Example: The Value for Health State 21354
Full health (11111)		Full Health=1
Mobility level 2	-0.096	-0.096
Mobility level 3	-0.122	
Mobility level 4	-0.237	
Mobility level 5	-0.322	
Self-Care level 2	-0.089	0
Self-Care level 3	-0.107	
Self-Care level 4	-0.220	
Self-Care level 5	-0.261	

Table 8: EQ-5D-5L cTTO Calculation

US cTTO		Example: The Value for Health State 21354
Usual Activity level 2	-0.068	
Usual Activity level 3	-0.101	-0.101
Usual Activity level 4	-0.255	
Usual Activity level 5	-0.255	
Pain/Discomfort level 2	-0.060	
Pain/Discomfort level 3	-0.098	
Pain/Discomfort level 4	-0.318	
Pain/Discomfort level 5	-0.414	-0.414
Anxiety/Depression level 2	-0.057	
Anxiety/Depression level 3	-0.123	
Anxiety/Depression level 4	-0.299	-0.299
Anxiety/Depression level 5	-0.321	
Health State Index Score		=1-0.096-0-0.101-0.414-0.299=0.090

Abbreviations: cTTO = composite time trade-off; EQ-5D-5L = 5-level EuroQol-5 Dimension

If data for some but not all dimensions are missing at a specific time point, data for the missing dimension(s) from the last available assessment prior to the time point with missing data will be used in the US cTTO calculation. If all dimensions are missing, the last available US cTTO score prior to the time point with missing data will be used.

The VAS records the respondent's self-rated health on a vertical, visual analog scale where the endpoints are labeled, "The best health you can imagine" for 100 and "The worst health you can imagine" for 0. Missing values will be coded as "999." If there is a discrepancy between where the respondent has placed the X and the number written in the box, number in the box will be used for VAS.

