4.1.4. Handling of Dropouts or Missing Data

No imputation will be performed for missing baseline values. For missing postbaseline data not due to IEs, no imputation will be performed.

To derive duration of disease, partial date of diagnosis will be imputed as follows:

- If day is missing, it will be imputed to the "01"
- If day and month are missing, they will be imputed to "January 01"

Partial concomitant medication start dates and AE start dates will follow the same imputation rule to derive study phase.

Missing outcome data due to the COVID-19 pandemic (eg, dropout due to COVID-19) is assumed missing-at-random (MAR).

Missing outcome data due to dosing pause is assumed MAR.

Missing data for quality-of-life (QoL) instruments will be handled as specified in the instructions for each instrument in Section 6.3.

The following may occur during the study:

- Receipt of additional standard-of-care therapy (LN cohort only)
- Treatment discontinuation (LN and IgAN cohorts)
- Dosing pause

The handling of IEs is detailed in each analysis section.

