4.3.1. Secondary Endpoints

4.3.1.1. Percentage Change in Proteinuria from Baseline to Week 50 (Both Cohorts)

The percentage change from baseline in proteinuria at Week 50 will be analyzed using a mixed-effect model for repeated-measures (MMRM) using all available data up to Week 50 (either complete or partial). The data after the intercurrent events will be treated as missing. The model will include change from baseline in log-transformed proteinuria as the response variable and fixed, categorical effects of treatment sequence group, randomization stratification factor, visit, and treatment sequence group by visit interaction as well as a fixed, continuous effect of baseline log proteinuria as a covariate. An unstructured covariance matrix will be used to model the correlations among repeated measurements within each participant. If this analysis fails to

converge, a first-order autoregressive covariance matrix will be used. The Kenward-Roger approximation will be used to estimate denominator degrees of freedom.

For the LN cohort, the treatment effect will be evaluated for the ALXN2050 180 mg bid and placebo treatment groups using a contrast for treatment group-by-visit term at Week 50. The point estimate and 2-sided 90% CI for the mean difference of log-transformed proteinuria will be back-transformed (via exponentiation) to obtain the GMR and corresponding 2-sided 90% CI. The values will then be expressed as percentage change in adjusted geometric mean of proteinuria at Week 50 relative to baseline. The treatment effect will be evaluated for the ALXN2050 120 mg & 180 mg bid and placebo treatment group in the same model mentioned above.

For the IgAN cohort, participants initially randomized to the placebo treatment group will switch to receive either ALXN2050 180 mg bid or ALXN2050 120 mg bid at Week 26. Percentage change from baseline in proteinuria at Week 50 will be summarized for each treatment sequence group from the MMRM analysis and no formal treatment comparison will be made. In addition, percentage change from re-baseline (ie, Week 26) in proteinuria at Week 50 will also be summarized for each treatment sequence group descriptively.

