4.4.5. EQ-5D-5L (Both Cohorts)

The 5-level EuroQol-5 Dimensions (EQ-5D-5L) is a self-reported standardized instrument to measure health-related QoL and has been used in a wide range of health conditions. The EQ-5D-5L is defined by 5 dimensions: mobility, usual activities, self-care, pain/discomfort, and anxiety/depression. A 0 to 1 health state index score (or utility score), where 0 indicates a health state equivalent to death and 1 indicates perfect health, will be calculated from individual health profiles using a US TTO value set. Negative values indicate health states considered worse than death.

Refer to Section 6.3 for a more detailed description of the EQ-5D-5L calculation and scoring methods.

For both cohorts, the EQ-5D-5L index score and visual analog scale (VAS) score will be summarized by treatment group at baseline and each post-Baseline time point using descriptive statistics for continuous variables for the observed value as well as the change from baseline.

Change from baseline in EQ-5D-5L scores at Weeks 26 and 50 will also be analyzed using the same MMRM method, and no formal treatment comparison will be made. The point estimate and 2-sided 95% CI for the change from baseline of EQ-5D-5L scores will be presented. Data collected on or after receipt of additional standard of care therapy or treatment discontinuation will be assumed missing and handled in the MMRM model as MAR.

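### SAP 6.3.2 carries forward a wholly missing EQ-5D-5L index score although 4.4.5 puts that index into an MMRM under MAR, and the SAP does not say which rule comes first

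*SAP*

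**What the plan says.** SAP 6.3.2 gives two carry-forward rules for the EQ-5D-5L index. For a partly answered questionnaire it borrows the blank items from before: "If data for some but not all dimensions are missing at a specific time point, data for the missing dimension(s) from the last available assessment". For a questionnaire missed altogether: "If all dimensions are missing, the last available US cTTO score prior to the time point with missing data will be used". There is no limit on how far back the score may come from. The visual analogue scale has no such rule; its section says only "Missing values will be coded as" 999.

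SAP 4.1.4 sets a general default, "For missing postbaseline data not due to IEs, no imputation will be performed", but sends missing quality-of-life data to Section 6.3. The no-imputation statement at the head of 4.4 also gives way where something else is specified. The carry-forward rule is therefore operative.

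SAP 4.4.5 then takes the same score into a model: "Change from baseline in EQ-5D-5L scores at Weeks 26 and 50 will also be analyzed using the same MMRM method". The method it points to, in 4.3.1.1, works "using all available data up to Week 50 (either complete or partial"). On intercurrent events 4.4.5 says "Data collected on or after receipt of additional standard of care therapy or treatment discontinuation will be assumed missing" and, in the same sentence, that these data "will be assumed missing and handled in the MMRM model as MAR". SAP 4.1.4 separately assumes MAR for outcomes missing because of COVID-19 or the dosing pause.

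**The concern.** An index value filled with an earlier score is not missing as far as the model is concerned. An MMRM earns its MAR validity by leaving the gap open and using the participant's other visits and the fitted covariance. Carry-forward closes the gap with a fixed number, assumes no change after the last completed questionnaire, and counts that number as a measurement. Both rules cannot govern the same value.

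At stake are the Week 26 and Week 50 estimates of mean change in the index and their 95% confidence intervals. Reproducibility is also at stake, because two programmers could follow this SAP faithfully and produce different tables.

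**Working it through.** The plan states no figure on this point. Its Table 8 scoring example does reproduce (1 − 0.096 − 0 − 0.101 − 0.414 − 0.299 = 0.090), so scoring of a complete questionnaire is not in dispute.

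**The two possible orders**

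| Order | Post-event values | Questionnaires missed for other reasons |
|---|---|---|
| Set post-event data to missing, then score | Refilled with a pre-event score, so 4.4.5 is not carried out | Filled |
| Score, then set post-event data to missing | Left missing, as 4.4.5 intends | Still filled, including COVID-19 and dosing-pause gaps that 4.1.4 assumes MAR |

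Each order leaves a defect. The first is the larger.

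**What the rule does to individual participants**

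- A participant with only a Day 1 index gets a change of exactly 0 at every later visit.
- In the IgAN cohort, EQ-5D-5L is collected on Day 1 and at Weeks 6, 12, 26, 38 and 50 (protocol Tables 2 and 4). The placebo group switches to ALXN2050 after the Week 26 assessments. If Week 38 is missed, the pre-switch Week 26 score stands as an on-drug value. If Weeks 38 and 50 are both missed, it becomes the Week 50 result. Measured from the Week 26 re-baseline, the change is then 0 by construction.

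**Comparison with the other instruments.** SF-36 (4.4.4) and FACIT-Fatigue (4.4.10) use the same MMRM and MAR wording, but their scoring rules (6.3.1.7 and 6.3.3) recover items within one visit. Only the EQ-5D-5L index borrows across visits, and no reason is given.

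**Standard error, rough count.** If every missing Week 50 value is filled, the model counts n values where n_obs exist. The reported SE relative to a complete-case SE is √(n_obs/n), which depends only on the missing proportion. Using an LN arm of 30:

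- 10% missing (the dropout rate in SAP Section 5): √(27/30) = 0.949, about 5% too small.
- 15% missing (an assumption, not in the documents): √(25.5/30) = 0.922, about 8% too small.

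These are ceilings. An MMRM without carry-forward recovers information from earlier visits. If only Week 50 is missing and its correlation with the preceding visit is r, the variance is about s²[(1 − r²)/n_obs + r²/n], and the ratio becomes 1/√[(1 − r²)/(n_obs/n) + r²]. For assumed values of r:

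| r | 10% missing | 15% missing |
|---|---|---|
| 0.4 | 1/√1.093 = 0.956 (4%) | 1/√1.148 = 0.933 (7%) |
| 0.6 | 1/√1.071 = 0.966 (3%) | 1/√1.113 = 0.948 (5%) |
| 0.8 | 1/√1.040 = 0.981 (2%) | 1/√1.064 = 0.970 (3%) |

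**Bias, illustration only.** One LN arm of 30 was simulated with visits at Weeks 8, 16, 26, 34, 42 and 50. All remaining inputs are assumptions: SD of change 0.18, AR(1) correlation 0.6, a linear mean gain, and MAR dropout concentrated in participants below average at the preceding visit. All missing values were carried forward. Bias in the Week 50 mean change was:

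| Dropout | True gain 0.05 | 0.10 | 0.15 |
|---|---|---|---|
| 10% | −0.013 | −0.016 | −0.018 |
| 20% | −0.025 | −0.031 | −0.035 |
| 30% | −0.038 | −0.047 | −0.054 |

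An estimate valid under MAR, without carry-forward, was within about 0.002 of the truth throughout.

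**The case against.** The best defence is that the two rules do different jobs and can be read in sequence. Section 6.3.2 is a scoring instruction for unanswered questionnaires; the MAR sentence in 4.4.5 concerns answers that were collected after an event and are then set aside. Score first, blank second, and the model does see post-event values as missing. Carry-forward for quality-of-life data is also a declared exception in 4.1.4, not a slip. The endpoint is exploratory, 4.4 calls its analyses descriptive, and 4.4.5 makes no formal treatment comparison.

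Much of this stands. A reader might infer that the MMRM never meets a missing EQ-5D-5L value. The documents do not support that: no order is stated, the MAR sentence covers only data after the two named events, the visual analogue scale is not carried forward, and an index with no earlier score cannot be. Nor should 8% be read as the expected error, since it needs an assumed missing rate, uncorrelated visits and every gap filled.

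The sequential reading does not clear the plan, however. It is one reading among two, and under it the questionnaires missed for other reasons are still entered as observed, against the MAR assumption that 4.1.4 itself makes for COVID-19 and the dosing pause. Being declared does not make the exception compatible with the model.

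**Conclusion.** The point holds for the index score. A whole-score carry-forward rule is in force for an endpoint analysed by MMRM under MAR, and whichever rule is applied first, some imputed values enter the model as observations. The effect is a mean change pulled toward the earlier score and a standard error that is too small: at most about 5% at 10% missing and about 8% at an assumed 15%, or roughly 2% to 7% for between-visit correlations of 0.4 to 0.8. The simulated bias depends wholly on assumed inputs and shows direction and order of size only. How many questionnaires are missing, including through the dosing pause, is not in the documents.

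This is a minor point. No test, power statement or stated decision rule uses the index. The clearest practical harm is that a pre-switch IgAN placebo score can be presented as an on-drug result.

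**What to change.** In SAP 6.3.2, delete the sentence that carries the last index score forward when all dimensions are missing. Alternatively, keep it but bar carried index scores from the MMRM input and from the change-from-baseline summaries. In 4.4.5, state that a wholly missing index is left missing and handled by the MMRM as MAR, and that values set to missing after an intercurrent event are not refilled by any scoring rule.

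Treatment of a single blank dimension can be left to the sponsor; discarding four answered dimensions because one is blank is debatable and is not needed to resolve this point.

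The cost is two or three SAP sentences and the matching programming specification. Protocol 10.10.1 contains no carry-forward rule, so no protocol change and no new data are needed.
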